8.4.2.3 Week 5 (Day 29±1)

The following procedures will be conducted and documented at this **office visit**:

- Measure systolic blood pressure, diastolic blood pressure, respiratory rate, pulse rate, and body temperature.
- Review the subject eDiary / back-up paper diary and provide re-training, if necessary.
- Supervised infusion of IgPro20. Supervised entry of infusion data in the subject eDiary / back-up paper diary.
- IgPro20 dispensation and IRT update.
- Review instructions for how to use pump for infusion of IgPro20, if necessary.
- Evaluate for AEs (including injection site reaction[s]), record any findings in the eCRF, and confirm that AEs have also been recorded in the subject eDiary / back-up paper diary. Re-train subjects to record AEs in the subject eDiary / back-up paper diary, if necessary.
- Review if subject has met definition of non-responder for this infusion parameter level.
- Record use of any concomitant therapy(ies).

8.4.2.4 Weeks 6 (Day 36±1), 7(Day 43±1) & 8 (Day 50±1)

The following procedures will be conducted and documented **at home**:

- Administer IgPro20. Infusion data should be recorded in the subject eDiary / back-up paper diary.
- Evaluate for AEs (including injection site reaction[s]) and record any findings in the subject eDiary / back-up paper diary.

8.4.2.5 Week 9 (Day 57±1)

The following procedures will be conducted and documented at this **office visit**:

- Measure systolic blood pressure, diastolic blood pressure, respiratory rate, pulse rate, and body temperature.
- Supervised infusion of IgPro20. Supervised entry of infusion data in the subject eDiary / back-up paper diary.
- IgPro20 dispensation and IRT update.
- Review instructions for how to use pump for infusion of IgPro20, if necessary.
- Review the subject eDiary / back-up paper diary and provide re-training, if necessary.
- Evaluate for AEs (including injection site reaction[s]), record any findings in the eCRF, and confirm that AEs have also been recorded in the subject eDiary / back-up paper diary. Re-train subjects to record AEs in the subject eDiary / back-up paper diary, if necessary.
- Review if subject has met definition of non-responder for this infusion parameter level.
- Record use of any concomitant therapy(ies).

8.4.2.6 Weeks 10 (Day 64±1), 11 (Day 71±1), 12 (Day 78±1)

The following procedures will be conducted and documented **at home**:

- Administer IgPro20. Infusion data should be recorded in the subject eDiary / back-up paper diary.
- Evaluate for AEs (including injection site reaction[s]) and record any findings in the subject eDiary / back-up paper diary.

8.4.2.7 Week 13 (Day 85±1)

The following procedures will be conducted and documented at this **office visit**:

-
- Measure systolic blood pressure, diastolic blood pressure, respiratory rate, pulse rate, and body temperature.
 - Review the subject eDiary / back-up paper diary and provide re-training, if necessary.
 - Supervised infusion of IgPro20. Supervised entry of infusion data in the subject eDiary / back-up paper diary.
 - IgPro20 dispensation and IRT update.
 - Review instructions for how to use pump for infusion of IgPro20, if necessary.
 - Evaluate for AEs (including injection reaction[s]), record any findings in the eCRF, confirm that AEs have also been recorded in the subject eDiary / back-up paper diary. Re-train subjects to record AEs in the subject eDiary / back-up paper diary, if necessary.
 - Review if subject has met definition of non-responder for this infusion parameter level.
 - Record use of any concomitant therapy(ies).

8.4.2.8 Weeks 14 (Day 92±1), 15 (Day 99±1) & 16 (Day 106±1)

The following procedures will be conducted and documented **at home**:

- Administer IgPro20. Infusion data should be recorded in the subject eDiary / back-up paper diary.
- Evaluate for AEs (including injection site reaction[s]) and record any findings in the subject eDiary / back-up paper diary.

8.4.3 Manual Push Flow Rate & Pump-Assisted Volume Cohorts

8.4.3.1 Week 1 (Day 1)

The following procedures will be conducted and documented at this **office visit**:

- Review inclusion/exclusion criteria.
- Measure systolic blood pressure, diastolic blood pressure, respiratory rate, pulse rate, and body temperature.
- Collect blood sample for IgG trough level assessment (within approximately 1 hour before infusion).
- Train subjects on how to administer an infusion of IgPro20.

- Train subjects on how to use the subject eDiary / back-up paper diary.
- Supervised infusion of IgPro20 via whichever method the subject will use (either pump or manual push). Supervised entry of infusion data in the subject eDiary / back-up paper diary.
- IgPro20 dispensation and IRT update.
- Evaluate for AEs (including injection site reaction[s]) and record any findings in the eCRF. Train subjects to record AEs in the subject eDiary / back-up paper diary. Confirm that AEs have been recorded in the subject eDiary / back-up paper diary.
- Record use of any concomitant therapy(ies).

8.4.3.2 Weeks 2 (Day 8±1), 3 (Day 15±1) & 4 (Day 22±1)

The following procedures will be conducted and documented **at home**:

- Administer IgPro20 (weekly for pump-assisted infusions, more frequent than weekly [2-7 days per week] for manual push). Infusion data should be recorded in the subject eDiary / back-up paper diary.
- Evaluate for AEs (including injection site reaction[s]) and record any findings in the subject eDiary / back-up paper diary.

8.4.3.3 Week 5 (Day 29±1)

The following procedures will be conducted and documented at this **office visit**:

- Measure systolic blood pressure, diastolic blood pressure, respiratory rate, pulse rate, and body temperature.
- Review the subject eDiary / back-up paper diary and provide re-training, if necessary.
- Supervised infusion of IgPro20 (weekly for pump-assisted infusions, more frequent than weekly [2-7 days per week] for manual push). Supervised entry of infusion data in the subject eDiary / back-up paper diary.
- IgPro20 dispensation and IRT update.
- Review how to use pump for infusion of IgPro20, if necessary.
- Evaluate for AEs (including injection site reaction[s]), record any findings in the eCRF, and confirm that AEs have also been recorded in the subject eDiary / back-up paper diary. Re-train subjects to record AEs in the subject eDiary / back-up paper diary, if necessary.

- Review if subject has met definition of non-responder for this infusion parameter level.
- Record use of any concomitant therapy(ies).

8.4.3.4 Weeks 6 (Day 36±1), 7 (Day 43±1) & 8 (Day 50±1)

The following procedures will be conducted and documented **at home**:

- Administer IgPro20 (weekly for pump-assisted infusions, more frequent than weekly [2-7 days per week] for manual push). Infusion data should be recorded in the subject eDiary / back-up paper diary.
- Evaluate for AEs (including injection site reaction[s]) and record any findings in the subject eDiary / back-up paper diary.

8.4.3.5 Week 9 (Day 57±1)

The following procedures will be conducted and documented at this **office visit**:

- Measure systolic blood pressure, diastolic blood pressure, respiratory rate, pulse rate, and body temperature.
- Review the subject eDiary / back-up paper diary and provide re-training, if necessary.
- Supervised infusion of IgPro20 (weekly for pump-assisted infusions, more frequent than weekly [2-7 days per week] for manual push). Supervised entry of infusion data in the subject eDiary / back-up paper diary.
- IgPro20 dispensation and IRT update.
- Review instructions for how to use pump for infusion of IgPro20, if necessary.
- Evaluate for AEs (including injection site reaction[s]), record any findings in the eCRF, and confirm that AEs have also been recorded in the subject eDiary / back-up paper diary. Re-train subjects to record AEs in the subject eDiary / back-up paper diary, if necessary.
- Review if subject has met definition of non-responder for this infusion parameter level.
- Record use of any concomitant therapy(ies).

8.4.3.6 Weeks 10 (Day 64±1), 11 (Day 71±1) & 12 (Day 78±1)

The following procedures will be conducted and documented at **home**:

- Administer IgPro20 (weekly for pump-assisted infusions, more frequent than weekly [2-7 days per week] for manual push). Infusion data should be recorded in the subject eDiary / back-up paper diary.
- Evaluate for AEs (including injection site reaction[s]) and record any findings in the subject eDiary / back-up paper diary.

8.4.4 End of Study

The scheduled end of study participation for an individual subject occurs during Week 13 on Day 85 ± 1 day for the Manual Push Flow Rate & Pump Assisted Volume cohorts (Week 17 on Day 113 ± 1 day for the Pump-Assisted Flow Rate Cohort). After that no further study-related procedures will be performed. The following procedures will be performed and documented at this **office visit**:

- Collect blood sample for beta-human chorionic gonadotropin for females of child-bearing potential.
- Perform a physical examination.
- Measure vital signs:
 - Systolic blood pressure, diastolic blood pressure, respiratory rate, pulse rate, and body temperature
 - Body weight
 - Height
- Collect blood sample for IgG trough level assessment (within approximately 1 hour before infusion).
- Collect blood samples for laboratory safety evaluation (biochemistry and hematology).
- Review and collection of subject eDiary / back-up paper diary and collection of eDiary device, if provisioned.
- Evaluate for AEs (including injection site reaction[s]) and record any findings.
- Record use of any concomitant therapy(ies).

Subjects who discontinue the study early will be asked to complete the End of Study procedures.

9. Adverse Events

9.1 Definitions

9.1.1 Adverse Event

As per the ICH guidelines, an AE is any untoward medical occurrence in a patient or clinical investigation subject administered a pharmaceutical product and which does not necessarily have a causal relationship with this treatment. An AE can, therefore, be any unfavorable and unintended sign (including an abnormal, clinically significant laboratory finding), symptom, or disease temporally associated with the use of a medicinal (investigational) product, whether or not considered related to the medicinal (investigational) product.

The period of observation for AEs extends from the time the subject gives informed consent until the End of Study (see [Section 9.4](#) for further details).

Adverse events may include:

- Exacerbation (ie, an increase in the frequency or severity) of a pre-existing condition. Illness present before study entry should be recorded in the medical history section of the eCRF and only be reported as an AE if there is an increase in the frequency or severity of the condition during the study.
- A clinical event occurring after consent but before IgPro20 administration.
- Intercurrent illnesses with an onset after administration of IgPro20.

Adverse events do not include:

- Events identified at Screening that meet exclusion criteria.
- Medical or surgical procedures (the condition that leads to the procedure is the AE).
- Situations where an untoward medical occurrence has not taken place. For example:
 - Planned hospitalizations due to pre-existing conditions, which have not worsened.
 - Hospitalizations that occur for procedures not due to an AE (eg, cosmetic surgery).
 - Hospitalizations for a diagnostic procedure where the hospital stay is less than 24 h in duration or for normal management procedures (eg, chemotherapy).
- Overdose of IgPro20 or any concomitant therapy that does not result in any adverse signs or symptoms.

For laboratory safety parameters, any instances of absolute values being outside the reference range or changes at any visit after study start that are considered by the investigator as clinically significant must be recorded in the eCRF as AEs. In addition, at the investigator's discretion, any changes or trends over time in laboratory parameters can be recorded in the eCRF as AEs if such changes or trends are considered to be clinically relevant, even if the absolute values are within the reference range.

Laboratory findings do not need to be reported as AEs in the following cases:

- Laboratory parameters already beyond the reference range at Screening, unless a further increase/decrease can be considered an exacerbation of a pre-existing condition.
- Abnormal laboratory parameters caused by mechanical or physical influences on the blood sample (eg, in vitro hemolysis) and flagged as such by the laboratory in the laboratory report.
- Abnormal parameters that are obviously biologically implausible (eg, values that are incompatible with life or outside the measuring range).
- An abnormal laboratory value that cannot be confirmed after repeat analysis, preferably in the same laboratory (ie, the previous result could be marked as not valid and should not necessarily be reported as an AE).

9.1.2 Adverse Event of Special Interest

Not applicable.

9.1.3 Serious Adverse Event

A serious adverse event (SAE) is defined as any untoward medical occurrence that at any dose:

- **Results in death** – The event must be the cause of death for the SAE to meet this serious criterion.
- **Is life-threatening** – The term “life-threatening” refers to an event in which the subject was at risk of death at the time of the event; it does not refer to an event that hypothetically might have caused death if it had been more severe.

- **Requires in-patient hospitalization or prolongation of existing hospitalization** – CSL considers “hospitalization or prolongation of existing hospitalization” for at least 24 h as the defining criterion for an SAE. Hospital admissions for planned surgery or for normal disease management procedures (eg, chemotherapy) are not considered as defining criteria for SAEs.
- **Results in persistent or significant disability or incapacity.**
- **Is a congenital anomaly or birth defect.**
- **Is medically significant** – A medically significant event is defined as an event that does not necessarily meet any of the SAE criteria, but which is judged by a qualified healthcare provider to potentially jeopardize the subject or require medical or surgical intervention to prevent one of the above outcomes listed as an SAE criterion.

Adverse events that do not fall into the above categories are defined as nonserious AEs.

9.2 Severity of Adverse Events

The severity of each AE (ie, nonserious and serious AEs) is to be assessed by the investigator as follows:

Severity	Definition
Mild	A type of AE that is usually transient and may require only minimal treatment or therapeutic intervention. The event does not generally interfere with usual activities of daily living.
Moderate	A type of AE that is usually alleviated with additional specific therapeutic intervention. The event interferes with usual activities of daily living, causing discomfort but poses no significant or permanent risk of harm to the subject.
Severe	A type of AE that interrupts usual activities of daily living, or significantly affects clinical status, or may require intensive therapeutic intervention.

CDISC SDTM Severity Intensity Scale for Adverse Event Terminology.

AE = adverse event.

If AE severity is not reported (missing), it will be conservatively assessed as a severe AE.

9.3 Causality of Adverse Events

The causal relationship of an AE to IgPro20 must always be assessed by the investigator. All AEs will be classified as either **related** or **not related** to IgPro20. If a causality assessment is not provided for an AE (including an SAE), the AE will be considered related to IgPro20.

The degree of certainty with which an AE is attributed to IgPro20 or an alternative cause (eg, natural history of the underlying disease, concomitant therapy) will be determined by how well the event can be understood in terms of:

- Known pharmacology of IgPro20.
- Clinically and / or pathophysiologically plausible context.
- Reaction of a similar nature previously observed with similar products, or reported in the literature for similar products as being product-related (eg, headache, facial flushing, pallor).
- Plausibility supported by the temporal relationship (eg, the event being related by time to administration or termination of treatment with IgPro20, IMP withdrawal or reproduced on rechallenge).

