9.6.1 Requirements for Reporting of Serious Adverse Events

The minimum reporting requirements for reporting of SAEs include:

- Identifiable subject.
- Suspected medicinal product and / or procedure.
- Event term.
- Identifiable reporting source.

In addition, the investigator must:

- Report all SAEs to the relevant Institutional Review Board / Independent Ethics Committee (IRB / IEC) within the timeframe specified by the IRB / IEC.
- Enter follow-up information in the eCRF until the SAE has resolved, or, in the case of permanent impairment, until stabilized.
- Ensure that the causality assessment for all SAEs is entered in the eCRF.

If the minimum requirements for reporting are fulfilled, the investigator should not wait to receive additional information to fully document the event.

In cases of death, the investigator should supply CSL and the IEC / IRB (as applicable) with any additional information as it becomes available (eg, autopsy reports and detailed medical reports).

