### 8.1 Missing Data

#### 8.1.1 Imputation of Non-Date Missing Data

Missing data occurs when any requested data is not provided, leading to blank fields on the collection instrument. These data will be indicated by the use of a “blank” in subject listing displays. Answers such as “Not applicable” and “Not evaluable” are not considered to be missing data and should be displayed as such.

Subjects with the designation of treatment relationship for AEs and serious AEs (SAEs) missing will have the worst realistic case assumed to impute the relationship: if relationship to study treatment is missing and the AE started on or after the first infusion of study treatment it will be assumed to be “Related” (worst case). If the AE with missing relationship to treatment started before the first infusion of study treatment, it will be considered as “Not Related” (realistic case). There will be no other imputation for missing data.

For variables which determine the proportion of subjects, all subjects in the SAF will be included in the denominator when calculating the percentages irrespective of whether their outcome may be missing.

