**Table 2: Minimum criteria for a valid infusion**

Pump-Assisted Volume Cohort		
Infusion Parameter	Definition Per Protocol	Modified Definition
Volume	Maximum volume administered per injection site is at least 95% of the planned max volume (i.e., 25 mL, 40 mL or 50 mL) for at least 1 injection site.	No modification
Flow rate	Not applicable	Not applicable
Dose	Total dose administered is at least 95% of the planned dose.	No modification

Pump-Assisted Volume Cohort		
Interruptions or stops	Not interrupted or stopped prematurely for any reason as documented in the eDiary.	May be stopped for technical reasons* only.
AEs	Not addressed.	No related AEs started during interrupted or stopped infusion.
*Technical reason: technical problem with any part of equipment (pump, syringe, tubing, needle, including needle placement) used for infusion.		

Pump-Assisted Flow Rate Cohort		
Infusion Parameter	Definition Per Protocol	Modified Definition
Volume	Not applicable	Not applicable
Flow rate	Injection site flow rate is at least 95% of the planned flow rate (i.e., 25 mL/h, 50 mL/h, 75 mL/h, or 100 mL/h) for at least one injection site.	No modification
Dose	Total dose administered is at least 95% of the planned dose.	No modification
Interruptions or stops	Not interrupted or stopped prematurely for any reason as documented in the eDiary.	May be stopped for technical reasons* only.
AEs	Not addressed.	No related AEs started during interrupted or stopped infusion.
*Technical reason: technical problem with any part of equipment (pump, syringe, tubing, needle, including needle placement) used for infusion.		

Manual Push Flow Rate Cohort		
Infusion Parameter	Definition Per Protocol	Modified Definition
Volume	The actual infusion volume is at least 95% of the planned infusion volume for that infusion day.	No modification
Flow rate	The actual infusion duration is not more than 1 minute or 10% (whichever is larger) longer than the calculated infusion duration based on the desired flow rate (i.e., 0.5 mL/minute, 1 mL/minute, or 2 mL/minute) and the actual volume infused.	No modification

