and will be presented by infusion parameter and cohort. The number of infusions irrespective of their validity as defined in Section 11.1 will be used as denominator for the assessment of tolerability. The total number of infusions within infusion parameter level and within cohort will be considered as denominator for the tolerability within infusion parameter level and within cohort, respectively. An infusion without severe local reactions is defined as no occurrence of a severe local reaction from the start date and time of an infusion until the start date and time of the next infusion or study end if this was the last infusion.

Local TEAEs will be identified by the MedDRA high level terms “administration site reactions NEC”, “infusion site reactions”, and “injection site reactions”. The MedDRA high level terms will be reviewed prior to database lock and the list of terms to be included into Local TEAEs will be updated. Local TEAEs will be included in all tables by using a virtual SOC called “Local Adverse Events”. In addition, the local TEAEs will also be presented by their MedDRA SOC “General disorders and administration site conditions”.

TEAEs will be sorted in descending order of total incidence by SOC and PT.

The summary will report for the Any TEAE row, each SOC, and each PT, the number of subjects with at least one TEAE, counted for the maximum reported severity in the table by severity. Local TEAEs will be reported only once in the Any row.

A listing of MedDRA SOC, PT, and verbatim text will be provided.

All AEs will be listed. TEAEs will be listed for the SAF. Other AE listings will use all available data. The listings will include the variables as specified in Section 7 and in addition MedDRA SOC, PT, and the verbatim, AE start and end date and time if available, duration of AE in days, severity, serious (yes or no), relationship to treatment (yes or no), outcome, action taken, and AE flags (TEAE, SAE, temporal relationship within 72h [AE72h]). Additionally, a listing of subject IDs for each individual PT will be produced.

The following listings will be provided:

- Non-TEAEs – all available data;
- TEAEs – SAF;
- Deaths – all available data;
- SAEs – all available data;
- AEs leading to study discontinuation – all available data;
- Local TEAEs – SAF;
- MedDRA SOC and PT with all AE verbatim – all available data;
- Subject IDs for each PT – all available data.

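### In the pump cohorts, the SAP's modified valid-infusion rule depends on relatedness to IgPro20 alone, so a stopped infusion with a site reaction attributed to needle or pump can count towards response

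*Protocol*

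**What the plan says.** **Causality.** Protocol 9.3 states: "The causal relationship of an AE to IgPro20 must always be assessed by the investigator". Each event is classed as related or not related to the product, weighed against alternative causes; the examples given are the underlying disease and concomitant therapy. The nearest mention of administration is a plausibility criterion about timing, "the event being related by time to administration or termination of treatment with IgPro20". Procedure appears as a possible suspect only in the minimum content of a serious adverse event report (protocol 9.6.1): "Suspected medicinal product and / or procedure". The SAP listings (11.4) carry one yes/no variable for relationship to treatment, and SAP 4.3 defines the study treatment as IgPro20.

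**What the study changes.** Subjects enter on a stable IgPro20 dose (protocol 4.1.1). The weekly dose stays the same, and only the infusion parameter under evaluation is raised (protocol 3.1).

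**Valid infusions.** For the pump cohorts, protocol Table 6 invalidates any interruption or early stop, whatever the cause. SAP 2.2 and Table 2 repeat that definition and set a modified one beside it. Under the modified definition a stop is allowed for a technical reason only, meaning a "technical problem with any part of equipment (pump, syringe, tubing, needle, including needle placement) used for infusion", together with the condition "No related AEs started during interrupted or stopped infusion". Both definitions also require at least 95% of the planned dose, at least 95% of the planned level at one or more sites, and no prohibited medication.

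**Use.** At least 3 valid infusions of 4 make a responder. A level succeeds at 33% responders, and the highest successful level in a cohort becomes the label recommendation (protocol 11.3.5, SAP 11.1).

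**The concern.** The two conditions in the modified definition look like separate safeguards: the stop must be technical, and no related event may have started. Because relatedness is asked only about the product, a single judgement that the needle or pump was to blame can satisfy both. Pain or swelling at the site during an infusion at a raised volume or rate is what the study sets out to observe. If it is attributed to equipment, the infusion can still be credited to the level being tested.

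The investigator making the judgement knows the level under test, and the result feeds an endpoint meant to drive a label change. The SAP also does not say which definition feeds the responder percentage. Section 11.1 sets out both and then refers back to response as already defined. Its introductory sentence still excludes interruptions, and SAP section 5 lists only the handling of missing severity as a change from the protocol. A reader cannot rule out that the modified definition decides success.

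**Working it through.** **1. The same event under each rule.** Take a pump infusion at a raised level that is stopped and resumed for a recorded needle problem. At least 95% of dose and level is reached, no prohibited medication is used, and a local reaction starts during the infusion.

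| Rule | Reaction recorded as related | Reaction recorded as not related |
|---|---|---|
| Protocol definition | invalid | invalid |
| SAP modified definition | invalid | valid |

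Only the lower right cell depends on the causality judgement. Manual Push has no interruption or adverse event criterion, so the question does not arise there.

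**2. The plan's own figure.** Inputs are 15 subjects, a 50% response rate, and success at 5 of 15 or more (protocol 3.1 and 11.1).

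P(X ≥ 5 | n = 15, r = 0.5) = 0.941, against the stated 94%. The figure reproduces and is not in dispute.

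**3. Distance to the threshold.** 4/15 = 26.7% fails and 5/15 = 33.3% passes. One reclassified subject moves the percentage by 1/15 = 6.7 points.

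**4. Illustration of size.** The documents give no rate for such infusions, so these inputs are assumptions: infusions and subjects are independent, all 15 subjects test the level, v is the per-infusion validity under the strict protocol rule, and a share f of the invalid infusions is re-counted as valid.

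- Validity after re-counting: q = v + f(1 − v)
- Responder probability: r = 4q³(1 − q) + q⁴
- Chance of success: P(X ≥ 5 | n = 15, r)

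| v | f | q | r | P(at least 5/15) |
|---|---|---|---|---|
| 0.45 | 0 | 0.450 | 0.241 | 0.286 |
| 0.45 | 0.10 | 0.505 | 0.320 | 0.552 |
| 0.45 | 0.20 | 0.560 | 0.407 | 0.800 |
| 0.50 | 0 | 0.500 | 0.312 | 0.527 |
| 0.50 | 0.10 | 0.550 | 0.391 | 0.761 |
| 0.50 | 0.20 | 0.600 | 0.475 | 0.914 |
| 0.61 | 0 | 0.610 | 0.493 | 0.934 |
| 0.61 | 0.10 | 0.649 | 0.561 | 0.979 |
| 0.61 | 0.20 | 0.688 | 0.630 | 0.995 |

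The last three rows start from the 61% that the documents use as the per-infusion validity matching a 50% response rate. There the chance of success rises from 93% to 98% or 99.5%. The large shifts occur where a level is close to 33% responders, because the curve is steep there.

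**The case against.** A reader might infer that 9.3 makes any reaction caused by the procedure not related. The text does not say so. Its examples of alternative causes name neither needle nor pump. Its criteria (plausible context, similar reactions seen before, timing) lean towards related for a site reaction, and protocol 1.4 lists local reactions among those seen with the product. A missing assessment also defaults to related: protocol 9.3 says so outright, and SAP 8.1.1 applies it "if relationship to study treatment is missing and the AE started on or after the first infusion of study treatment". The gap opens only if an investigator actively chooses equipment over product. The annotated eCRFs named in SAP section 3 were not available, so the exact wording of the causality item is unknown.

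The route is also narrow. The stop must be recorded as an equipment problem; one made because of pain does not qualify on a plain reading. The dose and level must still be reached, and the protocol definition is reported alongside.

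The fix can be called a design preference, since neither definition invalidates an uninterrupted infusion because of a reaction. Under it, a mild reaction during an infusion paused for a tubing fault would invalidate that infusion, while the same reaction without a pause would not.

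These points limit the concern but do not remove it. The asymmetry between paused and unpaused infusions already exists in both definitions. What stands is that, once an infusion has stopped, its validity can turn on an attribution question that leaves out the exposure being tested.

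**Conclusion.** The concern holds for the two pump-assisted cohorts under the SAP's modified definition. There, a local reaction during an interrupted infusion can be left out of the validity decision if it is attributed to needle or pump.

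Two stronger conclusions are not supported:

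- **That the responder percentages are biased upward.** This would require such infusions to occur, to be classed as not related, and the modified definition to drive the decision. The documents settle none of these.
- **That local reactions would go unreported.** Local TEAEs are identified by MedDRA term whatever their causality, tolerability counts severe local reactions over all infusions, and the 72-hour table does not use relatedness. The causally related rows in SAP 11.4 do use the product-only field, but no secondary endpoint rests on them.

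The size is unknown. On the assumptions shown, the effect could decide the outcome for a level near 33% responders and is small at the 61% planning value. The change is worth making because it is cheap and the endpoint leads to a label recommendation.

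**What to change.** 1. In SAP 2.2 and Table 2, modified definition, both pump cohorts: change the adverse event condition to require that no local TEAE of any causality and no related adverse event started during the interrupted or stopped infusion. The SAP already defines local TEAEs by MedDRA high level terms, and the existing rule already needs onset relative to the infusion, so no new data are required.
2. In SAP 11.1, state which definition drives the responder percentage and the 33% criterion and which is supportive. List the modified definition in SAP section 5 as a change from the protocol.
3. Where still feasible, word the causality item in protocol 9.3 and the eCRF as relation to IgPro20 or its administration. If it is too late for events already recorded, the first change alone closes the route for local reactions.

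The first two changes cost SAP wording before database lock. The third costs one wording change in the protocol and the eCRF. The downside is that some genuine equipment stops with an incidental local reaction would count as invalid, as they already do under the protocol definition, so responder rates under the modified definition may be slightly lower.
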